Study Description:	A double-blind, randomized, placebo-controlled clinical trial examining the efficacy and safety of Fecal Microbiota Transplantation (FMT) and high fiber supplementation in patients with active mild to moderate Ulcerative Colitis (UC). All enrolled subjects will provide serological, stool and mucosal specimen at each clinic visit to help further define the alterations in microbial profiles and immune cell function in response to psyllium fiber after FMT treatment.
Sample Size:	N=135, 45 subjects per study arm
Enrollment:	This study will enroll 135 subjects and screen up to 150 subjects.
Study Population:	All male and female participants at least 18 years of age with prior history of mild to moderate Ulcerative Colitis and willing to undergo standard of care colonoscopy to assess active disease for study eligibility.
Enrollment Period:	2019-2023
Study Design:	This is a randomized, double-blind, placebo-controlled clinical trial with the following treatment assignments: 
1. Investigational FMP250 (one-time) at week 0
a. Subjects in this group will also blindly receive placebo FMP250 at week 8 by flexible sigmoidoscopy.2. Investigational FMP250 (one-time) at week 0 + Psyllium fiber (2x/day for 8 weeks)
a. Subjects in this group will also blindly receive placebo FMP250 at week 8 by flexible sigmoidoscopy.3. Placebo FMP250 (one-time) at week 0 with or without Psyllium fiber (2x/day for 8 weeks)
a. Subjects in this group will also blindly receive investigational FMP250 at week 8 by flexible sigmoidoscopy. Subjects will blindly receive the investigational or placebo FMP250 treatment only if they meet all inclusion and exclusion criteria during the day 0 screening colonoscopy. Subjects will receive a follow-up phone call or return for a clinic visit every 2 weeks post-FMT until week 12. At week 8 post-FMT, all subjects will be evaluated by flexible sigmoidoscopy in the clinic. Stool and blood samples will be collected for research from subjects at day 0 prior to FMT, week 4 post-FMT, week 8 post-FMT, and

week 12 post-FMT. Mucosal biopsies will also be taken during the initial colonoscopy at day 0 and during the follow-up flexible sigmoidoscopy at week 8. Subjects randomized into the placebo cohort will receive investigational FMP250 and subjects randomized into the investigational cohort will receive placebo FMP250 by flexible sigmoidoscopy at the week 8 clinic visit (after week 8 endpoint data are collected). All subjects will return 4 weeks later at week 12 for a clinic visit. All subjects will be contacted for follow-up phone calls every subsequent 6 months for the next year.

Description of Site(s) Enrolling**Participants:**

The Jill Roberts Center for Inflammatory Bowel Disease
Gastroenterology and Hepatology at David H. Koch Center
Weill Cornell Medicine/ New York Presbyterian Hospital
[name]
[name]

Study Duration:

2019-2023

Participant Duration:

12 weeks + 1 year follow up

[figure not shown]
Study Drug Name:

FMT Lower Delivery Microbiota Preparation (FMP250)

Intervention Description:

Subjects will receive up to 250cc of blinded investigational or placebo FMP250 delivered by colonoscopy once at day 0. Placebo treatment group will receive investigational FMP250 while the investigational treatment groups will receive placebo FMP250 by flexible sigmoidoscopy at week 8.

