6.1.2.1 Screening Colonoscopy (Baseline, Week 0 Day 0)

- Urine pregnancy test as standard of care
- Standard of Care Colonoscopy for diagnostic purposes
 1. Mucosal biopsies taken for diagnostic and research purposes
- FMT delivery by colonoscopy for research purposes

1. If active disease, study physician will blindly administer placebo or investigational FMP250
- Stool and blood samples taken for research purposes, if not previously collected during screening period (days -28 to -3).

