6.1.2.2 Clinic Visit 3 (Week 8 ± 5 day(s))

- Medical history (AE evaluation)
- Medication history
- Physical exam
- Urine pregnancy test for research purposes
- Flexible Sigmoidoscopy for diagnostic purposes
 1. Mucosal biopsies taken for research purposes
 2. Subjects in placebo group blindly receive investigational FMP250 .
 3. Subjects in investigational groups blindly receive placebo FMP250
- Stool and blood samples taken for research purposes
- Standard of Care Testing
 1. Fecal Calprotectin
 2. Serological CBC, ESR, CRP, and CMP

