10.1 Response Criteria

10.1.1 Primary Endpoint Assessments

10.1.1.1 Mayo Scoring System³⁰

The Mayo Scoring System will be used for the assessment of ulcerative colitis activity. It is a composite score that ranges from 0-12 based on the following four categories: bleeding, stool frequency, physician assessment, and endoscopic findings. A partial Mayo Score ranges from 0-9 and can also be utilized if no endoscopic visualization is available to assess disease activity.

Study subjects will be evaluated by a full Mayo score at day 0 and week 8, and a partial Mayo score at the week 4 clinic visit. Both clinical response and remission will be evaluated at week 8 post-FMT. Clinical response is described as a reduction of the Mayo score by >3 points and >30% reduction from baseline with an accompanying decrease in the sub-score for rectal bleeding of at least 1 point. Clinical remission will be defined by Mayo score \leq 2 without any sub-score >1, and Mayo endoscopic sub-score 0-1.

Table 2. Mayo Scoring System for the assessment of ulcerative colitis activity.

Stool frequency [†]
0 = Normal no. of stools for this patient
1 = 1 to 2 stools more than normal
2 = 3 to 4 stools more than normal
3 = 5 or more stools more than normal
Subscore, 0 to 3
Rectal bleeding [‡]
0 = No blood seen
1 = Streaks of blood with stool less than half the time
2 = Obvious blood with stool most of the time
3 = Blood alone passes
Subscore, 0 to 3
Findings on endoscopy
0 = Normal or inactive disease
1 = Mild disease (erythema, decreased vascular pattern, mild friability)
2 = Moderate disease (marked erythema, lack of vascular pattern, friability, erosions)
3 = Severe disease (spontaneous bleeding, ulceration)
Subscore, 0 to 3
Physician's global assessment [§]
0 = Normal
1 = Mild disease
2 = Moderate disease
3 = Severe disease
Subscore, 0 to 3

* The Mayo score ranges from 0 to 12, with higher scores indicating more severe disease. Data are from Schroeder et al.²⁴

† Each patient serves as his or her own control to establish the degree of abnormality of the stool frequency.

‡ The daily bleeding score represents the most severe bleeding of the day.

§ The physician's global assessment acknowledges the three other criteria, the patient's daily recollection of abdominal discomfort and general sense of well-being, and other observations, such as physical findings and the patient's performance status.

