12.4 Analysis of Endpoints

12.4.1 Analysis of Primary Endpoints

1. Clinical response at week 8 post-FMT, as defined by the reduction of the Mayo scoring system by >3 points (+30% reduction) with an accompanying decrease in the sub-score for rectal bleeding of at least 1 point (Section 10.1.2.2).

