12.4.2 Analysis of Secondary Endpoints

- a. Clinical remission at week 8 post-FMT, as defined by Mayo score ≤ 2 without any sub-score >1
- b. Endoscopic response or remission, as defined as a Mayo endoscopic sub-score 0-1 with at least a 1-point reduction from baseline or a Mayo endoscopic sub-score of 0
- c. Safety will be assessed by:
 1. Subject mucosal biopsies, stool and blood testing.
 2. Subject symptomatology via medical interview, physical exam, and Mayo score and change in standard UC medications.
 3. Number and type of treatment related adverse events
 4. Number and type of disease-related complications such as hospitalizations, surgeries and endoscopies, medical complications, and mortality.

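### Endoscopic sub-score read by colonoscopy at day 0 and by flexible sigmoidoscopy at week 8, with no rule on which segment is scored: the secondary endoscopic endpoint can be met without healing

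*Combined protocol and SAP*

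**What the plan says.** The day-0 visit is a "Standard of Care Colonoscopy for diagnostic purposes" (6.1.2.1), and the endoscopic entry criteria in 4.2 are read at that examination. The week-8 visit is a "Flexible Sigmoidoscopy for diagnostic purposes" (6.1.2.2), and the Synopsis applies it to everyone: "all subjects will be evaluated by flexible sigmoidoscopy in the clinic".

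Both readings enter the same instrument: "Study subjects will be evaluated by a full Mayo score at day 0 and week 8" (10.1.1.1). In Table 2 the item "Findings on endoscopy" carries 0 to 3 of the 12 points. Neither the table nor the text names a segment, a worst-segment convention, or a restriction to bowel seen at both visits. Section 4.2 sets a minimum disease extent of 15 cm and no maximum.

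Two endpoints use a change from baseline that includes this item:

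- Primary (10.1.1.1, 12.4.1): "Clinical response is described as a reduction of the Mayo score by >3 points and >30% reduction from baseline", together with "an accompanying decrease in the sub-score for rectal bleeding of at least 1 point".
- Secondary endoscopic response or remission (12.4.2 b): "a Mayo endoscopic sub-score 0-1 with at least a 1-point reduction from baseline", or alternatively a week-8 sub-score of 0.

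Clinical remission (12.4.2 a) is a week-8 state and uses no baseline value.

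**The concern.** A change score assumes that the same thing was measured twice. Here the baseline reading can draw on the whole colon and the week-8 reading only on the distal part. If the worst visible segment is scored, the worst grade over a shorter length cannot exceed the worst grade over the full length. Any mismatch therefore runs towards apparent improvement.

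At stake are the credibility of the endoscopic response rates, which are a named secondary objective (1.2.2), and to a lesser degree the precision of the primary comparison.

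**Working it through.** **1. Secondary endoscopic endpoint, artefact alone.** Entry requires a baseline endoscopic sub-score of at least 1. Suppose nothing heals and the fall comes only from the shorter view:

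| Day 0 (colonoscopy) | Week 8 (sigmoidoscopy) | First limb (0-1 and fall of at least 1) | Second limb (0) |
|---|---|---|---|
| 1 | 0 | met | met |
| 2 | 1 | met | not met |
| 2 | 0 | met | met |
| 3 | 2 | not met | not met |
| 3 | 1 | met | not met |
| 3 | 0 | met | met |

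Five of the six possible falls satisfy the endpoint. A subject with unchanged grade 2 proximally and grade 1 distally reads 2 then 1 and counts as a responder. A baseline limited to the distal segment reads 1 then 1, which does not count. Matching corrects the two rows that end in 1. The three rows that end in 0 meet the second limb whatever the baseline is.

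**2. Primary endpoint, artefact alone.** On an integer scale a fall of more than 3 means at least 4. The endoscopic item can fall by at most 3 and cannot move the bleeding item. Enumerating all 166 sub-score combinations allowed by 4.2 (total 4 to 10, endoscopic at least 1, stool frequency or bleeding at least 1), none becomes a response through an endoscopic change alone. The 30% condition adds nothing here, since 4/10 = 40% already exceeds it.

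An artefact of 1, 2 or 3 points therefore needs a fall of at least 3, 2 or 1 points in the other items, including at least 1 in bleeding. Example, in the order stool, bleeding, endoscopy, global:

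- Baseline: 2 + 2 + 3 + 2 = 9.
- Week 8 with endoscopy truly unchanged: 1 + 1 + 3 + 1 = 6. The fall is 3, so no response.
- Week 8 with endoscopy read as 2: total 5. The fall is 4 (4/9 = 44%), so response.

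The footnote to Table 2 says the global assessment takes the other three items into account. An endoscopic artefact could spill into it, but the bleeding condition still applies.

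**3. Power.** Inputs from 12.1: 55% v 27%, 45 per arm, two-sided 0.05, about 80% power.

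The plan's figure reproduces with unpooled variance: n = (1.960 + 0.842)² × (0.55×0.45 + 0.27×0.73) / 0.28² = 44.5, so 45 per arm, with power 80.4%. With the pooled variance used by the chi-square test, power at 45 per arm is 78.0%. That is the base for the comparison below.

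Assume a share f of true non-responders in each arm is reclassified: p′ = p + f(1 − p). The difference becomes (1 − f) × 28 points.

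| f (assumed) | FMT+fiber | FMT alone | Difference (points) | Power | n per arm for 80% |
|---|---|---|---|---|---|
| 0 | 55.0% | 27.0% | 28.0 | 78.0% | 48 |
| 2% | 55.9% | 28.5% | 27.4 | 75.9% | 50 |
| 5% | 57.3% | 30.7% | 26.6 | 72.7% | 54 |
| 10% | 59.5% | 34.3% | 25.2 | 67.4% | 61 |

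With equal true rates of 27% in both arms, the exact type I error stays between 4.7% and 5.4% for f from 0 to 20%.

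**4. Which f is plausible.** Because of step 2, f is a product: the share of non-responders with a worse proximal than distal grade, times the share of those who are near-misses with a bleeding fall. Purely as illustration, f = 10% needs something like 25% × 40%. The documents give neither share.

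**The case against.** Several points weigh against the concern.

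- **The documents do not say that the baseline sub-score is the worst segment anywhere in the colon.** Endoscopists may already score the distal bowel at both visits. This stands: the loss of proximal disease from the follow-up score is a possibility left open, not something the plan prescribes.
- **Section 2.1 gives rectal involvement in 95% of cases,** so most subjects will have disease in view at week 8. This limits the problem but does not remove it. What matters is whether the proximal grade is worse than the distal one.
- **A reader might infer that the switch of instrument by itself creates primary-endpoint responders.** It cannot; step 2 shows why. Subjects who enter with bleeding 0 cannot respond at all, and those with missing week-8 data are counted as failures (12.1). Applying f to every non-responder is therefore generous, and the 67% power at f = 10% has no support in the documents.
- **A reader might infer a false treatment effect.** The procedures are the same in every arm and the week-8 assessor is blinded (7.12). The expected result is dilution. A chance imbalance in disease extent remains possible because there is no stratification (12.3).
- **A reader might count clinical remission as affected in the same way.** Remission and the sub-score-of-0 limb are week-8 states, so a matched baseline would leave both unchanged.
- **Matching has a cost.** A subject with total Mayo 4 whose single endoscopic point is seen only proximally would have an efficacy baseline of 3 and could never fall by more than 3. Real proximal healing would earn no credit.

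**Conclusion.** The point holds in a limited form. The two visits use different examinations, and no rule matches the segment scored. Under the plan as written, the first limb of 12.4.2 b can be met with no healing.

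The primary endpoint is exposed only through borderline subjects with a bleeding fall of at least 1 point. Under the assumed 2% to 5% reclassification, equal in both arms, power goes from 78% to between 76% and 73% and the difference from 28.0 to between 27.4 and 26.6 points. For the endoscopic endpoint the documents give no planning rate. By the same formula, an equal share g of reclassified non-responders shrinks any arm difference by the factor (1 − g).

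This rests on three things the documents do not state: that the baseline score can reflect bowel beyond sigmoidoscopic reach, how far that reach extends, and how often proximal disease is the worse. The conclusion is about inflated rates and some loss of power, not about a spurious benefit.

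**What to change.** State in 10.1.1.1 that the endoscopic sub-score used for change-from-baseline endpoints is the worst score within the flexible-sigmoidoscopy range at both visits. Record it at the day-0 colonoscopy as a field separate from the full-examination score, before the week-8 result is known. Refer to this definition in 12.4.1 and 12.4.2 b.

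Leave eligibility on the full examination. Report the same endpoints with the full-colonoscopy baseline score as a sensitivity analysis, so that any dependence on the convention is visible.

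The cost is one form field and a few sentences, with no extra procedure. The drawbacks are that proximal healing earns no credit and that a few subjects with proximal-only disease will have a lower efficacy baseline than their eligibility score. The change does not touch clinical remission or the sub-score-of-0 limb. If distal endoscopy raters already score only the shared segment, the sentence simply records current practice.

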1.1 Study Schematic

1.2 Study Objectives

1.2.1 Primary Objective

To assess if a dietary prebiotic supplementation (psyllium husk powder) in addition to FMT is superior to FMT or prebiotics alone to achieve clinical response in patients with mild to moderate Ulcerative Colitis compared to FMT or prebiotic alone.

1.2.2 Secondary Objective(s)

To assess if a dietary prebiotic supplementation in addition to FMT compared to either alone is superior in achieving clinical remission, endoscopic response or endoscopic remission, histologic response or remission rates.

To assess clinical response / remission and endoscopic response and remission of Fecal Microbiota Transplantation (FMT) for the management of active mild to moderate Ulcerative Colitis compared to placebo.

1.2.3 Exploratory Objective(s)

To define the microbial determinants of successful microbial manipulation therapy from mucosal, blood and stool samples collected at day 0 prior to FMT and week 8 post-FMT.

To define the impact of diet on the clinical and microbiome outcomes of Fecal Microbiota Transplantation (FMT) for the management of active mild to moderate Ulcerative Colitis compared to FMT or prebiotic alone.

2. Background

2.1 Ulcerative Colitis

Ulcerative colitis (UC) is a type of inflammatory bowel disease (IBD) characterized by recurring episodes of inflammation limited to the mucosal layer of the colon. This chronic disease may even extend to all divisions of the large intestine and in 95% of its cases it involves the rectum¹. The highest prevalence of UC is reported in Europe (505 cases per 10,000 in Norway) and North America (286 per 100,000 in USA)² with approximately 38,000 new cases each year³. The severity of this illness ranges from mild well-controlled symptoms to severe uncontrolled manifestations which require hospitalizations, blood transfusions, surgical interventions, and may even cause death.

Current treatment for UC relies heavily on drug therapies to target host factors and immune suppression for the management of symptoms, prevention of relapses, and induction of remission. Aminosalicylates are the first line therapy for newly diagnosed mild to moderate UC. Although safe and effective in mild to moderate UC, few alternatives exist, and non-compliance is commonplace. Patients who relapse often require escalation to immunomodulators or steroid therapy, which similarly have limited safety profiles. Steroids are efficient for induction therapy; however, they are known to have significant side effects and do not provide benefit for maintenance therapy. Immunomodulators, such as azathioprine and 6-mercaptopurine, similarly have a significant side

effect profile and limited efficacy in inducing remission. They increase the risk of lymphoma and other malignancies, and may result in bone marrow toxicity and hepatotoxicity^{4,5}. Mainstay of treatment for patients with UC who fail 5-ASA therapy are anti-tumor necrosis factor drugs (anti-TNFs), anti-integrin therapy (vedolizumab) and the janus kinase inhibitor tofacitinib, which are often efficacious with a clinical response rate reported to be as high as 70%⁶. Aside from vedolizumab, these therapies carry serious potential adverse effect profiles⁷⁻⁹. Furthermore, all have significant cost. Although there are numerous medications available for the management of UC, patients commonly become steroid-dependent and/or refractory to medical management and eventually require surgery¹⁰. Patients with poorly controlled UC are often desperate for a different method to control their symptoms due to the tremendous pain and suffering, loss of productivity, and disease-associated financial burdens.

Patients with IBD, including UC, harbor various genetic variants in genes regulating immune system function¹¹. These variants can increase susceptibility to abnormal immune responses to microorganisms within the gut resulting in persistent inflammation and the debilitating inflammation of UC. Although the etiology of UC is not well understood, the presence of certain beneficial bacteria can prevent disease in experimental animal models of colitis while the loss of these bacteria or overgrowth of other types can trigger induction of inflammatory responses and debilitating symptoms of IBD¹². The vast majority of treatment modalities for UC target host factors of inflammation. Despite substantial research efforts to understand the role of commensal bacteria in disease and pathogenesis, the therapeutic role for microbial manipulation in active UC is less well defined. Although antibiotics are used in the treatment of infectious complications of UC, their role for induction or maintenance therapy is unsupported by several different clinical studies. Therapeutic manipulation of intestinal microbiota can be achieved by other methods than antibiotics.

2.2 Fecal Microbiota Transplant (FMT)

FMT is an emerging therapy that transfers healthy donor fecal bacteria to patients suffering from GI illnesses with the goal of re-establishing a healthy intestinal bacterial community in those patients¹³. FMT has shown to be effective in the management of various diseases, most notably Clostridium difficile infections (CDI). A randomized control trial from 2013 in the New England Journal of Medicine evaluated the use of FMT in the management of CDI. The results were promising: an overall cure of 15 out of 16 patients (94%)¹⁴.

There are 3 major clinical trials that have looked at the safety and efficacy of FMT for the management of UC. In the first randomized, placebo controlled clinical trial by Rossen et. al, 50 patients with active UC (23/25) received FMT (donor stool) or placebo (autologous stool) via nasoduodenal delivery twice during the 12 weeks study period¹⁵. Analysis showed 41% vs 25% efficacy with no statistical differences between the groups¹⁵. Moayyedi et al. enrolled 75 study participants who received donor FMT or placebo (water) weekly enemas for 6 weeks¹⁶. 24% of patients who received FMT showed clinical response compared with 5% in placebo group and the difference between the groups was significant¹⁶. Paramsothy et al.'s study delivered donor FMT or placebo in 85 (42/43) patients via colonoscopy followed by 5 times per week enema for 8 weeks¹⁷. Primary outcome was reached by 27% of patients from FMT group compared with 8% in placebo group with significant differences between the groups¹⁷. These clinical findings indicate that despite the variation of delivery and dosage, FMT appears to be safe and effective for induction and remission of UC and can be included as an adjunctive therapeutic modality for management of the disease.

Our collaborative team recently completed a pilot study at Weill Cornell Medicine aimed at assessing the safety, clinical efficacy, and microbial engraftment of single FMT delivery by colonoscopy for active UC¹⁸. We performed a single-center, prospective, open-label pilot study to evaluate the safety and

efficacy of two-donor fecal microbiota preparation (FMP) delivery by colonoscopy. The primary outcome was clinical response at week 4 with secondary endpoints including clinical remission, mucosal healing at week 4 and safety profile. Overall, 34 patients were screened, and 20 patients were enrolled. Seven patients (35%) achieved a clinical response (Mayo score ≥ 3 and a bleeding subscore ≤ 1) by week 4. Three patients (15%) were in clinical remission at week 4 (Mayo score ≤ 2 and no subscore > 1), and two of these patients (10%) achieved mucosal healing (endoscopy subscore of 0). Paired analysis showed a significant improvement in Mayo score (Median decrease of 1.5, $p = 0.03$) and endoscopic subscore (Median decrease of 0.5, $p = 0.002$).

Further microbiome analysis revealed that signatures of donor-derived microbiota correlate with clinical response¹⁸. Taxonomic analysis revealed enrichment of *Ruminococcus*, *Odoribacter*, and *Christensenellaceae* in healthy donors and responders, but absent in patients with active disease. In contrast, patients who did not respond to treatment had failed to eradicate *Fusobacteria*, *Finegoldia* and *Collinsella*. To determine the fecal microbial composition and function at species/strain level, we performed metagenomic sequencing of a complete set of three samples (donor, recipient pre, recipient post) from three responder patients, who had met the primary endpoint of our pilot FMT trial. Relative abundances of microbial species were determined by Metaphlan2 and protein encoding genes profiling were determined by HUMAnN2 pipeline. Analysis of the previously identified transferrable genus of *Ruminococcus* revealed, that of the several species and strains present in the patient samples, abundance of only *Ruminococcus* torques was significantly enriched in responders. Collectively, this data revealed that response to single *colonoscopic* delivery correlated with engraftment of key species of transferrable bacteria in the responder patients. Further studies are required to determine factors that enhance the engraftment of these bacteria and increase the efficacy of this therapy.

